## 8.1 Study visits

This section describes study visits. Each visit will take place face-to-face, in clinics. More detailed information about assessments is summarised in Table 7.

### Baseline

#### Visit 1

(at baseline)

- Informed consent
- Eligibility check and confirmation
- Contact details
- Collection of baseline data:
  - Concomitant medication (relevant to condition) and relevant medical history
  - Demographic information
  - Clinician global severity assessment
  - Scarring assessment (VASS, clinical examination)
  - Vulval development and scarring (in adolescents and children)
  - Condition specific QoL (VQLI or CDQLI)
  - Health related QoL assessed by EQ-5D-5L in adolescents/adults and CHU-9D in children
  - Bespoke resource use questionnaire and healthcare questionnaire
- Clinical photographs, or clinical diagram if consent for photographs not taken
- Randomisation

#### Clinical photographs

Photographs will be taken at baseline for patients who consent to this, to assess scarring. Photographs will not be a mandatory requirement as some patients are hesitant due to the intimate nature of LS. Parents of children with LS are less likely to consent to photographs. Photographs taken up to 1 month prior to baseline appointment can be accepted, if the patient had no active disease during this period. If a photograph is not taken, clinicians will be asked to document a detailed clinical diagram (using a predefined schematic diagram) for comparison. Images taken at the baseline will remain in participant's medical notes and will not be sent to NCTU. Subsequent clinical examinations will assess changes against the baseline photo/diagram. Blinded assessments of scarring (or failure of normal anatomical development as appropriate) will be assessed at 12 and 24 months comparing to baseline clinical photographs.

### Follow up between clinic visits

Number of flares (primary outcome) and time to first flare (secondary outcome) will be captured throughout the first 12 months of the study. The primary outcome will be collected every two weeks via text/email/app (as per participant preference). An automated text message/email/app notification prompt will be sent to remind participants to complete their data entry with reminders for those who have not completed. The data collected via these methods will be linked to a web-browser page which is a direct interface to the trial database, REDCap. For the small proportion of patients who do not have a smartphone or computer, a member of the research team will telephone call to collect the information.

### Visit 2

(at 3 months)

- EQ-5D-5L in adolescents/adults and CHU-9D in children
- Condition specific Quality of Life will be assessed via VLQI or CDLQI
- Clinical global severity assessment – assessed by treating clinician
- Vulval development and scarring (in adolescents and children)
- Concomitant medication (relevant to condition)
- Bespoke resource use questionnaire and healthcare questionnaire
- Adherence to treatment
- Change or cessation of therapy
- Adverse events

### Visit 3

(at 6 months)

- EQ-5D-5L in adolescents/adults and CHU-9D in children
- Condition specific Quality of Life will be assessed via VLQI or CDLQI
- Clinical global severity assessment – assessed by treating clinician
- Vulval development and scarring (in adolescents and children)
- Concomitant medication (relevant to condition)
- Bespoke resource use questionnaire and healthcare questionnaire
- Adherence to treatment
- Change or cessation of therapy
- Adverse events

### Visit 4

(at 12 months)

- EQ-5D-5L in adolescents/adults and CHU-9D in children
- Condition specific Quality of Life will be assessed via VLQI or CDLQI
- Clinical global severity assessment - assessed by treating clinician and blinded assessor
- Vulval development and scarring (in adolescents and children)
- Concomitant medication (relevant to condition)
- Bespoke resource use questionnaire and healthcare questionnaire
- Adherence to treatment
- Change or cessation of therapy
- Adverse events
- Scarring (VASS and examination) – by blinded assessor
- Acceptability of treatment
- Sexual function using Female Sexual Function Index (in adults only)

### Visit 5

(at 18 months)

- EQ-5D-5L in adults and CHU-9D in children
- Condition specific Quality of Life will be assessed via VLQI or CDLQI
- Clinical global severity assessment – assessed by treating clinician

- Vulval development and scarring (in adolescents and children)
- Concomitant medication (relevant to condition)
- Bespoke resource use questionnaire and healthcare questionnaire
- Adherence to treatment
- Change or cessation of therapy
- Adverse events

[figure not shown]
## Visit 6

(at 24 months)

- EQ-5D-5L in adolescents/adults and CHU-9D in children
- Condition specific Quality of Life will be assessed via VLQI or CDLQI
- Clinical global severity – assessed by treating clinician and blinded assessor
- Vulval development and scarring (in adolescents and children)
- Concomitant medication (relevant to condition)
- Bespoke resource use questionnaire and healthcare questionnaire
- Adherence to treatment
- Change or cessation of therapy
- Adverse events
- Scarring (VASS and examination) – by blinded assessor
- Acceptability of treatment
- Sexual function using Female Sexual Function Index (in adults only)
- VIN or vulval SCC assessment

## **8.2 Concomitant and Rescue Medications and Treatments**

Concomitant medication (on entry and during their participation), relevant to the condition, will be documented in the Electronic Case Report Form (e-CRF) (using generic name and trade name as appropriate) and also in the participant's medical records. Any changes to these treatments and dosage will be documented. In the event of flaring symptoms, the Investigator may use an escalation of treatment algorithm (plan) as described in the figure below:

*\*Refer to urgent assessment according to local protocols.*

Figure 2. Recommended rescue treatment algorithm

All concomitant medications present at screening/baseline and which do not interfere with the assessments should, where possible, be kept constant from screening/baseline throughout the study.

### 8.3 Compliance

Adherence (compliance) to the allocated treatment regimens will be assessed using a bespoke questionnaire at 3, 6, 12, 18 and 24 months.

### 8.4 Accountability for drugs

Participants will be given prescriptions to obtain their allocated treatment at either hospital or community pharmacies (depending upon which is usual practice at the individual sites) in the same way as their routine medication. Therefore, there will be no drug dispensing and accountability in this trial.

## 8.5 Management of study drug overdose

The risk of overdose of the TCS is very low. TCS can be safely applied to the whole body in a single dose with minimal risk of adverse reactions. There is however a risk of adverse reactions following long-term use of topical corticosteroid to localised areas of skin (e.g. skin thinning, telangiectasia) and these will be monitored during clinical examination at follow-up visits (or at an unscheduled trial visit, as necessary).

## 8.6 Urgent Safety Measures

An Urgent Safety Measure (USM) procedure will be initiated if any research participant is identified as being at risk of harm in relation to their involvement in a research project. Urgent action, which deviates from the approved protocol, is required to manage the event and protect the participant. If any urgent safety measures are taken the CI shall immediately and, in any event, no later than 3 days from the date the measures are taken, give verbal and written notice to the MHRA, the relevant REC and the sponsor, of the measures taken and the circumstances giving rise to those measures. The sponsor must then follow-up with notification in writing within three days of the action being taken. The notification should be in the form of a substantial amendment and should describe the event, the measures taken and justification for the measures taken.

USMs which originate from MHRA will be communicated expeditiously with sites by the PEARLS central trial office.

## 8.7 Trial assessments\*

Table 7. Data collection timepoints

Trial assessment	Source	Timepoint and visit number					
		Screening/baseline Visit 1	3 month Visit 2	6 month Visit 3	12 month Visit 4	18 month Visit 5	24 month Visit 6
Confirmation of eligibility	Medical notes/clinician/participant	X					
Consent	Participant	X					
Randomisation	Participant	X					
Medical history	Participant/medical notes	X					
Demographic information	Participant/medical notes	X					
Concomitant medication (relevant to condition only)	Participant	X	X	X	X	X	X
Number of flares and time to 1st flare	Participant	Starting 2 weeks from randomisation, every 2 weeks for 12 months					
Progression of scarring via photograph (optional), VASS and examination	Clinician	X **			X €		X €
Vulval development and scarring (adolescents and children)	X	X	X	X	X	X	X
Clinical global severity assessment	Clinician	X	X	X	X μ	X	X μ
Condition specific Quality of Life (VQLI or CDLQI)	Participant	X	X	X	X	X	X
Health related quality of life (generic utility instrument) (EQ-5D-5L in adolescents/adults or CHU-9D in children)	Participant	X	X	X	X	X	X
Sexual function using Female Sexual Function Index (adults only)	Participant				X		X
Acceptability of treatment	Participant				X		X
Adherence to treatment	Participant		X	X	X	X	X
Resource use (bespoke and healthcare)	Participant	X	X	X	X	X	X
VIN or vulval SCC	Clinician						X
Adverse effects of therapy	Participant, Clinician		X	X	X	X	X
Change/cessation of therapy	Participant		X	X	X	X	X
* Definition of age groups for purpose of assessments is described in section 4.4		° At 12 and 24 months assessed by blinded assessor					
** Assessed by photographs (if consented) or clinical assessment diagram		μ At 12 and 24 months assessed by treating clinician and blinded assessor					
€ Clinical assessment comparing to baseline photographs (if consent given for photographs) or to baseline clinical assessment diagram if consent for photographs not obtained							

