### Clinical effectiveness

- Progression of scarring assessed by blinded assessor at 12 and 24 months by comparing post randomisation to baseline photographs (if participant consented), or assessed clinically if consent has not been given for photographs:
  - Adults: scarring worsened (yes/no)
  - Children and adolescents: failure of normal vulval development (clinical assessment) and/or evidence of scarring (yes/no).
- Vulvar Architectural Severity Scale at 12 and 24 months post randomisation (VASS) [30].
- Time to first flare.
- Global clinical severity assessment of LS (5-point ordinal scale) at 3, 6, 12, 18 & 24 months, plus assessed by blinded assessor at 12 and 24 months.
- Condition specific QoL at 3, 6, 12, 18 & 24 months using:
  - Vulvar Quality Life Index (VQLI) (adults) [31]
  - Children's Dermatology Life Quality Index (CDLQI) (adolescents and children) [32].
- Sexual function (adults only) using Female Sexual Function Index [33] at 12 & 24 Months.

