### 5.1 Maintenance of randomisation codes and procedures for breaking code

The research staff randomising a participant won't be blinded to the allocation due to the nature of the treatment.

The outcomes to which an assessor will be blinded to treatment allocation will be scarring, assessed at 12 and 24 months. Global clinical severity will normally be reported by the site unblinded clinician at all time points but additionally it will be assessed by the blinded assessor at 12 and 24 months. The blinded assessor will be someone that is deemed by the PI as adequately qualified (and recorded on the delegation log) to examine and identify changes in participants with vulval LS. They will not be involved in any other trial activities. A blinded assessor will compare changes at 12 and 24 months against baseline photos or clinical assessment diagram. Where a blinded assessor is not available at the time of clinical assessment, assessment will be made subsequently by review either of the photos taken during the assessment or by comparison with the clinical diagram, and record findings. Revealing the treatment strategy allocation to the assessor should not be necessary as both involve topical steroids. However, in the unlikely scenario that assessors identify safety concerns, such as vulval cancer/pre-cancer, they will report to the site Principal Investigator (PI), who is unblinded, and who will inform NCTU as per the NCTU standard process.

The trial statisticians and Trial Steering Committee (TSC) members will be blinded to participant group allocations. An unblinded independent NCTU statistician will produce closed reports for the Data Monitoring Committee (DMC). No emergency unblinding processes are necessary. The Table 4 below describes which trial staff will be blinded/unblinded to the treatment allocation.

Table 4. Blinding status of the PEARLS trial staff

	Blinding status	Comments
Participant	Not blinded	Not practical due to trial design
Principal Investigator and other site staff	Not blinded	Not practical due to trial design
Clinical assessor at site	Blinded assessor	Scarring and global clinical severity assessment at 12 and 24 months
	Unblinded assessor	Global clinical severity at all time points and development of VIN or vulval SCC at 24 months
Chief Investigator	Blinded	The Chief Investigator will remain blinded to treatment allocation with an exception of participants recruited at their site.

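### Section 4.4 makes vulval development in under-16s a blinded 12- and 24-month reading, but the visit lists, section 5.1 and Table 4 leave its assessor open

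*Protocol*

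**What the plan says.** The protocol treats vulval development in under-16s in two ways.

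**Where the outcome is defined.** Section 4.4 sets the outcome out as "Progression of scarring assessed by blinded assessor at 12 and 24 months by comparing post randomisation to baseline photographs". Under that heading it gives the under-16 version: "Children and adolescents: failure of normal vulval development (clinical assessment) and/or evidence of scarring (yes/no". The synopsis has the same structure. The paragraph on clinical photographs in section 8.1 is explicit about development: "Blinded assessments of scarring (or failure of normal anatomical development as appropriate) will be assessed at 12 and 24 months".

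**Where the work is assigned.**
- Section 5.1 states: "The outcomes to which an assessor will be blinded to treatment allocation will be scarring, assessed at 12 and 24 months". It then adds global severity as read by both the unblinded clinician and the blinded assessor.
- Table 4 gives the blinded assessor one entry: "Scarring and global clinical severity assessment at 12 and 24 months".
- The lists for Visit 4 (12 months) and Visit 6 (24 months) in section 8.1 contain "Scarring (VASS and examination) – by blinded assessor". They tag global severity for both the treating clinician and the blinded assessor.
- The same two lists carry, as a separate line with no assessor named, the item that Table 7 words as "Vulval development and scarring (adolescents and children" (almost the same words in the lists). The line is worded identically at months 3, 6 and 18.

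**The concern.** A site runs its visits from the visit lists and the delegation of roles in section 5.1 and Table 4. Someone following those at 12 months would see two items that mention scarring. One is marked for the blinded assessor. The other also covers development and is unmarked, as it was at months 3 and 6, when no blinded assessor is scheduled. The natural course would be for the same clinician to keep recording it, and Table 4 shows that site staff other than the blinded assessor know the allocation.

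At stake is the blinding of a secondary outcome that serves the disease-progression objective. It concerns the age group that section 1.4 says was included because evidence there is especially scarce. Whether development has failed is a matter of clinical judgement in an open-label trial, so knowledge of the allocation could influence it.

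**Working it through.** No arithmetic applies. The check sets the passages side by side and follows the outcome rule.

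**Step 1: is development meant to be blinded?** Yes. In section 4.4 and the synopsis, the under-16 measure sits beneath a heading that names a blinded assessor at 12 and 24 months. The photographs paragraph in section 8.1 names development in its own right as a blinded assessment at those times.

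**Step 2: is it assigned to the blinded assessor?** Not by name.
- Section 5.1: scarring and global severity are named; development is not.
- Table 4, blinded row: scarring and global severity.
- Table 4, unblinded row: global severity and VIN or vulval SCC. Development is not here either.
- Visits 4 and 6: the scarring item and global severity are tagged; development with scarring in under-16s is not.

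**Step 3: could development be covered by the tagged scarring item?** The visit lists make that doubtful, because they put the two on separate lines and name assessors item by item. The protocol also lists development separately at baseline and in the withdrawal table (Table 5), where it stands apart from photographs, VASS and examination.

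**Step 4: what follows for the outcome?** The rule is and/or. Suppose the blinded assessor finds no scarring and another reader records failed development. The outcome is then positive on the second reading alone. So if development were read by someone who knows the allocation, that reading could decide the result even though the scarring part was blinded.

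**Step 5: which scarring reading counts?** The untagged item covers scarring as well as development. An under-16 participant may therefore have two scarring readings at 12 and at 24 months, one tagged and one not. The visit lists do not say which forms the endpoint.

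**Table 7** is left out of this chain. In the text as read from the PDF, the development row has an X where the source should be, and the footnote about the blinded assessor is attached to no cell. Either may be an extraction fault.

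**The case against.** The strongest reply is that the endpoint definition already settles the matter. Section 4.4, the synopsis and the photographs paragraph all place development under blinded assessment, and no passage says otherwise. Tables 2 and 3 use scarring, or progression of scarring, as the label for the whole outcome with no separate development row, so section 5.1 and Table 4 may use the word in the same broad sense. Visit lists are inventories of procedures, and a missing tag does not declare a reading unblinded. If it did, scarring in under-16s would be unblinded too, against section 5.1.

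Much of this stands. The intention is clear, and the umbrella reading of section 5.1 and Table 4 is plausible. It does not remove the ambiguity in the Visit 4 and Visit 6 lists, which name assessors for neighbouring items and omit one here. Nor can this be left to the SAP: who examines the participant is fixed at the visit, and an analysis plan cannot restore blinding afterwards.

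A reader might infer three stronger things that the documents do not support:
- **That development will be read unblinded.** The assessor is left open; no passage assigns it to an unblinded reader.
- **That Table 7 proves the omission.** The table may be damaged, so it shows nothing either way.
- **That a bias can be sized.** The protocol does not give the expected share of under-16s. The 7–15% in section 1.4 describes vulval LS cases in connection with an incidence peak at ages four to six, not recruitment to this trial. Nothing in the protocol supports a rate of false positive readings, and it specifies no analysis pooling the adult and under-16 measures.

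**Conclusion.** The point holds as an inconsistency between the outcome definition and the instructions that put it into practice. The protocol intends a blinded reading of vulval development in under-16s at 12 and 24 months, but does not clearly hand that reading to the blinded assessor. An unblinded reading could therefore decide the under-16 outcome, and the scarring reading that counts is not identified.

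Its reach is limited to one secondary outcome, in participants under 16, at two visits. The primary outcome and the adult scarring outcome are not affected. The conclusion rests on the visit lists, section 5.1 and Table 4 set against section 4.4 and the photographs paragraph. It assumes that sites work from the lists as written. It is a minor point, worth correcting because the correction is simple.

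**What to change.** Bring the operational passages into line with section 4.4 and the photographs paragraph:

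1. In section 5.1 and in the blinded-assessor row of Table 4, name vulval development in under-16s among the outcomes read blind at 12 and 24 months.
2. In the Visit 4 and Visit 6 lists, tag the development and scarring item for the blinded assessor.
3. State that only the blinded 12- and 24-month readings form the under-16 endpoint, and that readings at other visits are for monitoring.
4. Check the Table 7 footnote and the source cell of the development row against the original PDF. If the marker is missing there too, attach it to the 12- and 24-month cells.

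The cost is a wording change in a protocol amendment. The blinded assessor is already due to assess these participants for scarring at both visits, so no additional assessor or visit is needed. The change helps only for 12- and 24-month visits that have not yet taken place.

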## 8.8 Protocol Deviations and Violations

A protocol deviation can be defined as a move away from described procedures in the treatment regimen e.g. a missed dose, study visit missed or taking place later than planned leading to data collections being at time-points differing to the rest of the study population. Because PEARLS is a pragmatic trial, and the assessment windows are selected to mirror the clinical practice, delayed assessments will only be reportable routinely to the TMG/TSC but will not constitute towards protocol violations which will need to be reported immediately to the sponsor.

A protocol violation is a variation in practice from the protocol which will need to be assessed for their impact on safety of the trial participant and of the data integrity, because they:

- a. Reduce the quality or completeness of data (e.g. not using backups for database)
- b. Impact trial participant's safety, rights or welfare (e.g. randomising patient without prior consent or without fulfilling eligibility criteria, disclosing participants identifiable information to third parties without consent)

Protocol violations may on occasions lead to the protocol being altered via a substantial amendment or a trial participant being excluded from the trial.

Protocol deviations (apart from those deviated from assessment windows) and ALL violations must be reported immediately to the PEARLS Trial Office.

The CI will notify the Sponsor if a protocol or non-protocol violation has an impact, or a potential to have an impact, on participant safety or integrity of the trial data. The Sponsor will advise on appropriate measures to address the occurrence which may include reporting of a serious GCP, protocol, GDPR etc breach, internal audit of the trial and seeking counsel of the trial committees.

## 8.9 Criteria for terminating trial

The trial recruitment will be assessed following the internal pilot phase (see section 8.10) to determine the feasibility of recruitment according to agreed progression criteria. The review will be undertaken by the TMG and TSC and if recruitment figures meet the red or amber categories, see Table 8, additional strategies will be put in place to attempt to improve these. The Sponsor also reserves the right to discontinue the trial at any time for failure to meet expected enrolment goals, for safety or any other administrative reasons. The Sponsor shall take advice from the TSC and the funder as appropriate in making this decision. As such, on the recommendation of the TSC, the sponsor (in collaboration with the TMG) may stop the trial if emerging evidence of efficacy or major safety concerns arise, or if there are significant concerns regarding trial conduct. There should be proof beyond reasonable doubt for overall efficacy or major safety concerns (internal or external evidence) for the TSC and TMG to recommend the trial is stopped.

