### 6.1.3 Data Monitoring Committee

Independence is a key characteristic of a DMC where the committee members are completely uninvolved in the running of the trial and thus cannot be unfairly influenced (either directly or indirectly) by people, or institutions, involved in the trial. The role of the DMC is to monitor outcome data, safety data and other trial data and make recommendations to the TSC on whether there are any ethical or safety reasons why the trial should not continue. The safety, rights and well-being of the trial participants will be considered paramount, alongside the validity of the trial data. The DMC will also consider data emerging from other related trials, provided by the Sponsor or Funder. The DMC will operate in accordance with a trial specific charter.

The DMC will consist of an Independent Chair, an Independent Clinician and an Independent Statistician. The DMC will meet on a regular basis as specified in the DMC charter, e.g. yearly, more regularly, or on an ad-hoc basis, when a meeting may be held in urgent instances in response to safety concerns. The DMC members will be required to sign a 'conflict of interests declaration form'. Following the meetings, the DMC will make recommendations to the TSC.

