#### **15.5 Discontinuation of the trial by sponsor**

The Sponsor reserves the right to discontinue this trial at any time for failure to meet expected enrolment goals, for safety or any other administrative reasons. The Sponsor shall take advice from the TSC and DMC as appropriate in making this decision.

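### Section 8.9 sets one proof-level standard for recommending a stop, for efficacy or for harm, and omits the DMC; this does not fit sections 6.1.2, 6.1.3 and 15.5

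*Protocol*

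**What the plan says.** Protocol section 8.9 lets the sponsor stop the trial for emerging efficacy, major safety concerns or problems of conduct: "on the recommendation of the TSC, the sponsor (in collaboration with the TMG) may stop the trial". It then sets the evidence needed, "There should be proof beyond reasonable doubt for overall efficacy or major safety concerns", whether internal or external, "for the TSC and TMG to recommend the trial is stopped". The DMC does not appear in the section.

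The same section gives the sponsor a separate power with no evidential condition: "The Sponsor also reserves the right to discontinue the trial at any time for failure to meet expected enrolment goals, for safety", among other reasons. On advice for that decision, 8.9 says "The Sponsor shall take advice from the TSC and the funder as appropriate in making this decision". Section 15.5 restates the power in nearly the same terms but says "The Sponsor shall take advice from the TSC and DMC as appropriate in making this decision".

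Elsewhere, section 6.1.3 makes participants' safety, rights and well-being the DMC's first consideration, alongside the validity of the data, and has it "make recommendations to the TSC on whether there are any ethical or safety reasons why the trial should not continue". Section 6.1.2 has the TSC consider the DMC's recommendations and act on them as it sees fit under its charter. Section 10.3 sends confidential by-arm reports to the DMC. Section 5.1 states: "The trial statisticians and Trial Steering Committee (TSC) members will be blinded to participant group allocations".

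**The concern.** A demanding standard is easy to defend for efficacy, where an early stop costs precision and may fix an exaggerated estimate. Harm is usually treated differently, because waiting for certainty is paid for by participants. Section 8.9 makes no such distinction.

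This matters here for three reasons found in the protocol. Participants may be as young as 5 (7.4.1). The proactive arm is to use potent or superpotent steroid for 24 months whether or not symptoms are present (section 8). Section 2.6 concedes that the risk of adverse effects has been poorly quantified, and safety is a secondary objective in its own right (3.3).

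The section headed as the criteria for terminating the trial also leaves out the one committee set up to look at comparative safety data. A committee member who turned to 8.9 for guidance on a safety signal would find the strict standard and no mention of the DMC.

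**Working it through.** The protocol gives no numerical stopping boundary, so there is no figure to reproduce. The check sets the sections side by side.

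1. **Reach of the standard (8.9).** The sentence joins efficacy and major safety concerns under one requirement. It cannot be read as applying to efficacy alone.

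2. **Whose act it governs (8.9).** It governs a recommendation by the TSC and TMG. It governs neither the DMC's advice nor the sponsor's decision.

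3. **What each body sees.**
   - DMC: by-arm reports, including interim estimates of differences in efficacy or safety outcomes (10.3).
   - TSC: blinded (5.1).
   - TMG: mixed. Its members include the Chief Investigator and trial statisticians, whom Table 4 lists as blinded (the Chief Investigator except for their own site). They also include the trial manager and data manager (6.1.1), and Table 4 lists trial management and data management staff as unblinded. By-arm reports to the TMG are not described.

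4. **Standard at each step of a safety recommendation.**
   - DMC to TSC (6.1.3): any ethical or safety reason, with no proof requirement.
   - TSC response (6.1.2): consider and act as appropriate, with no stated standard.
   - TSC and TMG to sponsor (8.9): the proof standard.
   - Sponsor (8.9 and 15.5): may discontinue for safety at any time, with no stated standard.

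   The strict standard therefore sits at one step only, between the committee that has seen the data and the sponsor. Section 6.1.2 leaves open what is appropriate, and 8.9 is the only section that says what the TSC needs before it recommends a stop. Taken literally, it allows a TSC that has not seen the comparison to answer a DMC safety recommendation by saying that the harm is unproven.

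5. **Advisers on the sponsor's decision.** Section 8.9 names the TSC and the funder. Section 15.5 names the TSC and the DMC. The power described is the same, and only the TSC is on both lists.

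**The case against.** The strongest reply is that the DMC route already exists. Section 6.1.3 lets the DMC raise any safety reason, 6.1.2 obliges the TSC to consider it, and nothing in 8.9 restricts the DMC. On this view the sections deal with different bodies at different stages and do not collide. Other safeguards also work without the proof standard. The sponsor may stop for safety at any time, the Chief Investigator's response to a SUSAR may include halting the trial (11.8), and urgent safety measures are provided for (8.6). Operational rules may also sit in the DMC and TSC charters, which are not at hand. Both adviser lists are qualified by the words that advice is taken where appropriate, and neither claims to be complete.

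Much of this stands, and it limits the point to one of reconciliation. It does not remove the sentence in 8.9, which still tells the TSC to hold harm to the same standard as benefit at the step where DMC advice has to be passed on. A charter may add detail but does not correct the protocol's own text.

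Three stronger readings are tempting, and the documents do not support them:

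- **That 8.9 hands the decision to committees without by-arm data.** The committees recommend and the sponsor decides. The lack of by-arm data is stated for the TSC, but the TMG includes unblinded staff.
- **That the standard can be turned into a p-value, and so into a count of extra harmed participants.** The protocol gives no boundary and admits external evidence, so the standard calls for an overall weighing of evidence and is not a test. Any count would rest wholly on the reader's own assumption.
- **That the TMG should have no part in a recommendation to stop.** That is a preference about governance, not an error in the document.

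**Conclusion.** The concern holds as an inconsistency within the protocol. Section 8.9 applies one proof-level standard to efficacy and harm and omits the DMC. That does not fit the DMC's remit in 6.1.3 or the TSC's duty in 6.1.2, and the adviser lists in 8.9 and 15.5 differ for the same decision.

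Its size is qualitative. The exposure is a possible delay or refusal at the TSC step if 8.9 is applied literally, and the sponsor's unconditional power to stop for safety limits it. The conclusion rests on the protocol wording alone and assumes only that a committee might follow 8.9 as written. It does not imply that the DMC is prevented from acting or that participants have no other protection.

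**What to change.** - In 8.9, limit the proof standard to stopping for efficacy.
- In 8.9, state that for safety the TSC considers recommendations made by the DMC under 6.1.3 without that standard, with a cross-reference to 6.1.2 and 10.3.
- Name the same advisers to the sponsor, including the DMC, in 8.9 and 15.5. Whether the funder is also listed is for the sponsor to settle, provided that both sections agree.
- Check that the DMC and TSC charters match the revised text.

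The cost is redrafting. No further data, participants or analyses are needed. The one downside is a somewhat higher chance of pausing the trial on a safety signal that later proves to be chance.
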